staff, etc.) within the practice. They will then complete a monthly REDCap survey reporting aggregate information regarding total time spent on project-specific activity (see “*PDSAandTimeCostSurvey...*” document).

Additionally, to monitor study staff efforts during this phase (to parallel surveys completed by practice champions), study staff will participate in the completion of a weekly “*Study Staff Time Survey*” (see step 4 for further detail).

Again, for participating █ practice sites, the 6-month intervention (including the Practice Time/Cost Survey and Study Staff Time Survey described above) will be extended by 3-5 months depending upon the specific location, to optimize vaccine intervention efforts and data collection during the peak of the COVID season.

4. *Participate in learning collaborative meetings* on a monthly basis with the study team. The vaccine champions from all participating intervention sites, along with the study team, will meet together as a group to discuss current COVID-19 information, intervention strategies/tips and overall project progress.

Step 3) Compare intervention vs. control practices:

Using the “RE-AIM” framework (see Table 4) we will compare intervention practices to control practices using multiple data sources. We will focus on one primary outcome and multiple secondary outcomes.

Primary Outcome: Following the conclusion of phase 2 (6-month duration), we will assess the “Effectiveness” of the intervention by comparing intervention group COVID-19 vaccination rates against control group COVID-19 vaccination rates.

Secondary Outcomes: Following the conclusion of phase 2 (6-month duration), we will assess the remaining “RE-AIM” domains including “Reach,” “Adoption,” “Implementation,” and “Maintenance.”

Table 4: Summary of Outcome Measures and Tools

RE-AIM Category	Outcome Measure(s)	Data Source
Reach	
• Number of patients seen in the practice within study period.• Number of providers/nurses/staff completing the training modules.	EHR data & training attendance records

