Effectiveness	
 Primary Outcome: Rate of COVID-19 vaccination (intervention vs control) Secondary Outcomes: 
 COVID-19 vaccination rates by subgroups including (i) insurance groups, (ii) race/ethnicity, (iii) number of pregnancy, (iv) vaccine in prior year Flu and Tdap vaccination rates by subgroups including (i) insurance groups, (ii) race/ethnicity, (iii) number of pregnancy, (iv) vaccine in prior year 	EHR data
Adoption	
 Number and proportion of personnel involved in the VAX-MOM office changes (receiving MOC credit, attending in-office meetings) 	Training attendance records
Implementation	
 Provider and office staff perceptions of feasibility, acceptability, barriers and facilitators to implementation, adherence to intervention, perceived time and cost, and impact on patient flow. Perceived strength of vaccine recommendations. Perceived adherence to staff checking whether vaccine is due. Costs of implementing interventions 	Post-Intervention Survey & Time/Cost Survey
Maintenance	
 Sustainability 	Post-Intervention Survey

Details for EHR data extraction:

- **EHR Measure Description:** We will work with health system EHR report builders and our experienced analysts to build EHR reports which evaluate vaccination coverage at participating sites (see Table 5).

Baseline data was previously gathered during STUDY00007624, STUDY00005115 and STUDY00004408. The remainder of this data (COVID intervention data), as well as any missing baseline data from the protocols listed above, will be gathered under the current protocol STUDY00007717.

Table 5. Data obtained from EHR for women with live births during intervention period

(NOTE: any data missing from the baseline period may also be gathered during Phase 2)

Primary Information	
 COVID-19 vaccination status (both dates and type) Flu vaccination status (dates) Tdap vaccination status (dates)
----------------------------	--

Additional Information: Patient Demographics	
 • DOB • MRN • Date of Delivery • GA at delivery • Race/ethnicity 	
 • Insurance • Language • Parity • High risk status • Other social determinants
Additional Information: Practice Demographics	
 • Site • Provider type (resident, midwife, MD) 	

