Surveys will be e-mailed to providers and select nurses by project staff using the secure web application REDCap (see “*IntroEmail_PostInterventionSurvey...*” document). E-mail addresses will have previously been obtained from the health system liaison or vaccine champion and uploaded to the REDCap platform. After initial survey distribution, if the subject does not click on the survey link embedded within the e-mail, the REDCap platform will automatically disseminate reminder e-mails to the subject (identical content as initial invite e-mail). Once clicked, the survey link will first take potential respondents to the Survey Information Sheet for review (see “Consent Process” section for more details), and if they agree, will then allow them to continue to the full survey. Surveys will be sent in 3 “waves” in order to allow subjects from each health system to view their own system-specific Information Sheet (e.g., [REDACTED] subjects will first see the [REDACTED] Info Sheet, followed by the full survey). Subjects may answer survey questions at their own pace and may stop and restart at any time. At the conclusion of the survey, they will receive an automated confirmation message to assure them that the process is complete.

Step 4) Evaluate cost of the VAX-MOM COVID-19 intervention:

[figure not shown]
Practice Time & Cost Survey (see “*PDSAandTimeCostSurvey...*” document): A survey aimed at evaluating the amount of time and money devoted to VAX-MOM COVID-19 intervention activities will be sent by the study coordinators via REDCap to the vaccine champion for each site on a monthly basis. The survey will be completed by the vaccine champion using their best time/cost estimates pertaining to the month prior.

Study Staff Time Survey (see “*StudyStaffTimeSurvey...*” document): A survey aimed at evaluating the efforts of VAX-MOM COVID-19 study staff will be sent to study personnel on a weekly basis via REDCap.

Final Time & Cost Analysis:

Upon completion of phase 2 we will conduct a final time/cost analysis. Our two-fold cost measures are (a) total intervention cost to implement the VAX-MOM COVID-19 program aggregated at the three health-system level under a cost analysis and (b) cost per additional vaccination under a subsequent cost-effectiveness analysis.

[figure not shown]
Figure 1: Timeline of Intervention Phase Procedures

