17. DATA ANALYSIS PLAN

The primary outcome (receipt of 1+ COVID vaccine) is binary and our main explanatory variable will be an indicator for study arm. We will employ intent-to-treat analyses using generalized linear mixed models (GLMMs) with practice random effects, an approach recommended for group-randomized RCTs in which the goal is to estimate the causal effects of interventions on individuals, adjusted for clustering within groups. This method performs well in situations where the number of observations per cluster is large and for unequal cluster sizes. Models will assume a binomial distribution and a log link function in order to compare vaccination rates between study arms in terms of risk ratios. We will adjust for all practice-level variables included in the randomization balancing criterion, as well as patient-level race/ethnicity. Hypothesis tests will be two-sided with alpha = 0.05. Analyses will be performed

using SAS v. 9.4 (SAS Institute Inc., Cary, NC).

Power Analysis: We conservatively assume a control group vaccination rate of 50% (maximum variance). Adjusting for clustering of patients in practices, and assuming an intraclass correlation (ICC) of 1% (consistent with previous work), this sample size provides 80% power to detect an overall increase of 8.0 percentage point increase in vaccination rates between the QI intervention and control arms. This assumes a chi-squared test (a simplification of the planned mixed model analysis described above), an alpha of 0.05, and a sample size of 5,000 pregnant women organized into 16 practices per study arm.

Final Time/Cost Analysis:

Our two-fold cost measures are (a) total intervention cost to implement the VAX-MOM COVID program aggregated at the three health-system level under a cost analysis and (b) cost per additional COVID vaccination under a subsequent cost-effectiveness analysis. To derive a policy implication regarding the sustainability of programs, we will estimate costs and ICER estimates from the health system perspective.

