Costs: To make these cost measures comparable to similar past interventions of reminders and educational programs, we will estimate cost with one-year time horizon, excluding the cost to purchase, store and administer vaccines. We will estimate the total intervention cost, summing non-personnel costs (e.g., EHR hardware, software, and materials) and personnel costs. The personnel costs will distinguish research costs from intervention costs (e.g., practice-level meeting and collecting EHR data). The dollar values of these personnel costs will be calculated by multiplying “time efforts” (weekly reported by study personnel using a REDCap email survey) with the nationally representative “hourly-wage rates” by occupation codes of study personnel, derived from the Bureau of Labor Statistics. We are using this method in an NIH-funded R01 study (the STOP-HPV study) which involves a practice-level intervention to raise HPV vaccination rates and in the original VAX-MOM study; surveys take <1 minute to complete.

Cost-Effectiveness: We will develop a standard decision model for our cost-effectiveness analyses as conducted in our past studies. The effectiveness measures are the rates of COVID vaccination estimated under Aim 2b. We will estimate incremental cost effectiveness ratios (ICERs) for the intervention defined as: $ICER (Study \text{ vs } control) = (cost_{Study} - cost_{Control}) / (COVID \text{ vaccine rate}_{Study} - COVID \text{ vaccine rate}_{Control})$

In the numerator of the equation, the $cost_{Study}$ is standardized to be equal to average intervention cost per patient in a study arm to account for the potential sample size difference between study and control arms.

As explained above, this intervention cost will exclude the cost to purchase, store and administer vaccines, which is assumed to be identical among all practices. Applying the same assumption, the average cost for the control group ($cost_{Control}$) is zero. Using the developed standard decision model, we will conduct probabilistic analyses to generate point estimates and 95% CIs for ICERs and one-way sensitivity analyses to determine conditions for being lower than the thresholds of cost-effectiveness, e.g., healthcare-system based quality improvement

interventions to improve flu vaccination uptake targeting general populations (median ICER \$51 among 23 interventions) and healthcare workers (median ICER \$125 among 6 interventions) reported by a systematic review.

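### Section 17's personnel-cost rule has no term for practice staff time and is not reconciled with Step 4 and Table 4, which collect that time to cost the intervention

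*Combined protocol and SAP*

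**What the plan says.** Section 17 (Costs) gives an explicit valuation rule. The time input is effort "weekly reported by study personnel using a REDCap email survey". The wage input is an hourly rate "by occupation codes of study personnel, derived from the Bureau of Labor Statistics". Section 17 (Final Time/Cost Analysis) sets the viewpoint: "we will estimate costs and ICER estimates from the health system perspective". Section 17 (Cost-Effectiveness) puts the average intervention cost per patient in the ICER numerator, sets the control arm's cost to zero, and compares the result with median ICERs of $51 and $125 from a systematic review.

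Section 4 describes two separate time instruments. Of the Study Staff Time Survey, Step 4 says: "A survey aimed at evaluating the efforts of VAX-MOM COVID-19 study staff will be sent to study personnel on a weekly basis via REDCap". The Practice Time & Cost Survey is monthly and is filled in by each site's vaccine champion. Step 4 describes it as "A survey aimed at evaluating the amount of time and money devoted to VAX-MOM COVID-19 intervention activities". Under Step 2, item 3, the champion records who attends the feedback and PDSA discussions and in what role, then submits a survey "reporting aggregate information regarding total time spent on project-specific activity". Table 4 gives "Post-Intervention Survey & Time/Cost Survey" as the source for the Implementation row, which includes the cost of implementing the intervention.

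**The concern.** Both inputs to the Section 17 rule are confined to study personnel, and Section 17 never mentions the practice survey. Yet the intervention is carried out largely by practice personnel: the online module, the site meeting, monthly rate feedback, PDSA cycles, and the champion's further duties, including monthly learning collaboratives. At some sites this work continues for a further 3 to 5 months. For a health system deciding whether to sustain the programme, those hours are a real cost.

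An analyst who follows Section 17 word for word would leave the practice survey unused. An analyst who starts from Step 4 would include it. The plan does not say which is correct, so the choice could be made after the results are known.

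**Working it through.** **Comparing the passages**

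1. The survey in the Section 17 rule is weekly and completed by study personnel. Step 4 has one instrument of that kind, the Study Staff Time Survey. The practice survey is monthly and comes from champions, so it is not the source that the rule names.
2. Section 17 separates research from intervention costs and gives meetings at practice level as an example. The next sentence values these personnel costs from study-personnel reports and study-personnel wages. Read literally, it counts study staff hours at such a meeting and not the hours of the practice staff attending.
3. Step 4 is the cost-evaluation step. It presents the practice survey just ahead of the final time and cost analysis, and Table 4 also points to it. The data are therefore gathered for costing, but no rule values them or adds them in.

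**Direction**

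ICER = (average intervention cost per patient − 0) / (rate in intervention arm − rate in control arm). With a positive denominator, dropping any positive cost lowers the ICER.

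**Size (illustration only)**

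The documents state no cost, hours, wage or ICER for this trial, so there is no figure to reproduce.

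- From Section 17 (Power Analysis): an 8.0-point effect, 16 practices per arm and 5,000 women. The sentence does not settle whether 5,000 is per arm or in total, so 5,000 and 2,500 intervention women are both shown.
- Assumed: $30 to $80 per hour, and 10 to 100 omitted practice-staff hours per intervention practice.

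Increment = (practices × hours × wage) / (0.08 × intervention women).

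- Additional vaccinations: 0.08 × 5,000 = 400, or 0.08 × 2,500 = 200.
- At 25 h and $50/h: 16 × 25 × $50 = $20,000. This is $20,000 / 400 = $50, or $20,000 / 200 = $100, per additional vaccination.
- Low end: 16 × 10 × $30 = $4,800, which adds $12 or $24.
- High end: 16 × 100 × $80 = $128,000, which adds $320 or $640.
- Hours per practice at $50/h that add $51 with 5,000 women: 51 × 400 / (16 × 50) = 25.5. To add $125: 125 × 400 / (16 × 50) = 62.5.

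The increment depends on women per practice, and 5,000 / 16 = 2,500 / 8 = 312.5. The plan's 80% power is reproduced with 2,500 women in 8 practices per arm (design effect 1 + 311.5 × 0.01 = 4.115; power 0.7996). It is not reproduced with 16 practices per arm (0.977 with 5,000 women per arm, 0.945 with 2,500). The $50 figure therefore also holds under the reading that matches the stated power. The $100 figure rests on the pairing of 2,500 women with 16 practices.

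**The case against.** The strongest reply is that the plan does not exclude practice time. Step 4 collects practice time and money for the cost evaluation, Table 4 lists the survey as a source, and Section 17 itself mentions practice-level meetings. Section 4 also says that the staff survey is meant to run in parallel with the champions' surveys. On this view Section 17 merely lacks a cross-reference.

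Much of this stands. A reader might infer that the sponsor has decided to leave practice time out and that the reported ICER will be too low. The documents do not support that. They point to an intention to use the data, and understatement follows only if Section 17 governs. But Section 17 is not silent: it states a formula, and that formula gives practice hours no value.

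Two further inferences also go beyond the text:

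- **A falsely favourable comparison with $51 and $125.** The documents do not say whether those medians include practice staff time, and Section 17 says its costing choices aim at comparability with past interventions.
- **All the practice data are already in the monthly survey.** Section 4 records module completion and site-meeting attendance through a completion survey and rosters, with no hours mentioned. The monthly survey reports aggregate time, and its form is not among the documents.

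**Conclusion.** The point holds as a conflict within the plan. Section 17's rule covers study-personnel time only, while Step 4 and Table 4 collect practice time to cost the same intervention. Applied literally, Section 17 understates the intervention cost and the ICER from the health-system perspective. The direction is certain given zero control cost and a positive effect.

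The size cannot be determined from the documents. The assumed inputs span $12 to $640 per additional vaccination, and about 25 hours per practice at $50/h would add roughly as much as the lower comparator. This shows that the omission could matter; it does not estimate the bias. Only the secondary economic analysis is affected. The randomisation and the primary vaccination comparison are not.

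**What to change.** Revise the Costs paragraph of Section 17 so that intervention personnel and practice cost is the sum of:

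- practice time from the monthly Practice Time & Cost Survey × the wage for the practice occupation, by role where the form allows and otherwise with a stated role mix;
- module and site-meeting attendance counts × a stated duration × wage, unless the monthly survey is shown to include these hours already;
- non-research study-staff time × wage;
- practice expenses reported in the survey.

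Keep research-only time out. Do not add champion payments on top of champion time that has been valued. Section 12 pays champions for the same tasks ($50 for module and site-meeting support, $150 for the monthly PDSA and time/cost surveys), so adding both risks double counting, and part of the payment is for completing study surveys.

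Settle the rule before the cost data are analysed. The cost is a short revision, a check of whether the survey form splits time by role, a stated duration for the module and meeting, and a little more analysis. The reported ICER will be less favourable than under the literal rule.

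### Staff time is priced at hourly wages with no term for employer-paid benefits, although costs are to be from the health system perspective, so intervention cost is understated as written

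*Combined protocol and SAP*

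**What the plan says.** The costing rules are in section 17 (Data Analysis Plan) of the combined protocol and SAP.

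- **Perspective.** Under Final Time/Cost Analysis, with programme sustainability as the policy question: "we will estimate costs and ICER estimates from the health system perspective".
- **Personnel cost.** Under Costs: "The dollar values of these personnel costs will be calculated by multiplying" time, "weekly reported by study personnel using a REDCap email survey", by national "hourly-wage rates" "by occupation codes of study personnel, derived from the Bureau of Labor Statistics".
- **Total cost.** It is formed by "summing non-personnel costs (e.g., EHR hardware, software, and materials) and personnel costs".
- **Declared exclusion.** The total is estimated over one year, "excluding the cost to purchase, store and administer vaccines". No other exclusion is named apart from the separation of research costs from intervention costs.
- **Control arm.** Under Cost-Effectiveness, "the average cost for the control group ($cost_{Control}$) is zero".
- **Use of the result.** Probabilistic and one-way sensitivity analyses are planned, and the ICER is read against published medians of $51 and $125.

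The costing text mentions no benefits, fringe rate, total compensation or overhead.

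**The concern.** A wage is what the worker is paid. If the employer also pays benefits, an hour of staff time costs the health system the wage plus those benefits. The plan names the health system as the party whose costs count, then prices each hour at the wage alone. Benefits are not among the declared exclusions, so a reader would not know that they had been left out.

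Two stated outputs are affected: the total intervention cost, and the cost per additional vaccination. The programme described in section 4 relies heavily on staff time (training, site meetings, monthly feedback, PDSA cycles, learning collaboratives), so the personnel component is unlikely to be trivial, although the documents put no figure on it. The point concerns the price per hour and applies whoever's hours are counted.

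**Working it through.** The plan states no wage, hours, total cost or expected ICER, so it has no figure of its own to reproduce. The check is algebra on its definitions, with two assumed inputs.

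**Inputs from section 17**
- ICER = (cost per patient, study − cost per patient, control) / (vaccination rate, study − vaccination rate, control).
- Control cost = 0.
- Study cost = non-personnel cost + hours × wage.
- Benchmarks: $51 and $125.

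**Assumed inputs (not in the documents)**
- f, employer-paid benefits as a fraction of wages: 20% to 40%.
- s, personnel share of the wage-only cost: 50% to 100%.

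**Step 1: effect on cost.** Let C be the wage-only cost. Its personnel part is sC. Adding benefits makes that part sC(1 + f), so the loaded cost is C(1 + f·s).

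**Step 2: effect on the ICER.** With control cost at zero, the ICER is proportional to study cost. The loaded ICER is therefore the wage-only ICER × (1 + f·s), whatever the rate difference. For a positive difference, the wage-only ICER is the lower of the two.

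**Step 3: numbers.** The shortfall of the wage-only figure is 1 − 1/(1 + f·s).

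| f | s | Factor 1 + f·s | Wage-only figure too low by |
|---|---|---|---|
| 20% | 50% | 1.10 | 9.1% |
| 30% | 90% | 1.27 | 21.3% |
| 40% | 100% | 1.40 | 28.6% |

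**Step 4: where a benchmark could be crossed.** Dividing each benchmark by the factor gives the wage-only ICER that just reaches it after loading.
- $51: 51/1.10 = $46.36; 51/1.40 = $36.43.
- $125: 125/1.10 = $113.64; 125/1.40 = $89.29.

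A wage-only ICER above roughly $36-46 and up to $51, or above roughly $89-114 and up to $125, would move past the benchmark once benefits are added. Outside those bands it stays on the same side: $20 × 1.40 = $28, still below $51. This step holds the benchmarks fixed, which is fair only if they include benefits themselves.

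**The case against.** **The text is a short summary, and silence is not exclusion.** Rates derived from Bureau of Labor Statistics data might be loaded in practice, and where the plan wants a cost left out it says so. This stands in part: a reader might infer that the analysts will certainly omit benefits, and the documents do not settle that. But the plan gives an explicit formula, and in ordinary use an hourly wage rate does not include benefits. Followed as written, it leaves them out. If a loading is intended, one sentence resolves the matter.

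**The size is assumed.** This stands. A reader might infer that the shortfall passes one-for-one into total cost. That needs a personnel share of 100%, and the plan also counts hardware, software and materials.

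**The benchmarks may be wage-only too.** This also stands. A reader might infer that the programme would wrongly appear to meet the $51 or $125 benchmark. The documents do not say how the underlying studies were costed. If they used wages alone, loading one side would make the comparison less like-for-like. The total health system cost, a separate stated output, would still be low.

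**Comparability with past work justifies wages only.** The plan does say that the same method is used in two of the team's other studies. However, its comparability argument is attached to the one-year horizon and the vaccine-cost exclusion, not to the wage rate.

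**The one-way analyses cover it.** Only partly. Varying cost would show how far the ICER could rise before crossing a benchmark, but no parameters are listed, and a sensitivity analysis does not correct the reported base-case cost.

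**The error always favours the programme.** A reader might infer this, but it is too strong. For the ICER it requires a positive vaccination difference, and it describes this one component, not the net bias of the costing.

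**Conclusion.** The concern holds as a mismatch between the stated perspective and the stated unit price. With no term for employer-paid benefits, the formula understates total intervention cost to the health system, and it understates the ICER when the vaccination difference is positive. This direction rests on the ordinary meaning of a wage and on the employer paying some benefits.

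The size cannot be fixed from the documents. The 1.10 to 1.40 range (9-29% too low) depends wholly on the assumed values of f and s. An effect on the benchmark comparison is possible but not shown. The weight is modest: cost is a secondary measure, and the vaccination effect and its test are untouched.

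**What to change.** In section 17, under Costs:

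1. In the base case, price each hour at the wage plus a stated and sourced benefits factor, or at total hourly compensation by occupation.
2. Name that factor as a parameter of the one-way sensitivity analysis, with its range.
3. Report the wage-only result alongside, for comparison with the team's earlier studies and with the $51 and $125 medians, and say whether those medians include benefits if the source shows it.

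If the rates already carry a loading, state the factor and its source instead.

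The cost is one multiplier in the model and a sentence or two in the plan, with no new data collection. The downside is a slightly less favourable cost figure and a base case no longer computed exactly as in the earlier studies; the wage-only result preserves that comparison.

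### Vaccine costs do not cancel from the ICER when uptake differs between arms, so the planned ratio is a programme-only figure and not the declared health-system ICER

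*Combined protocol and SAP*

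**What the plan says.** Section 17, under Final Time/Cost Analysis, sets the perspective: "we will estimate costs and ICER estimates from the health system perspective". The stated purpose is a policy implication about whether such programmes can be sustained.

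The Costs paragraph then leaves out vaccine purchase, storage and administration and gives a reason: "To make these cost measures comparable to similar past interventions of reminders and educational programs".

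The Cost-Effectiveness paragraph defines the ICER as the arm difference in cost divided by the arm difference in COVID vaccination rate. The study-arm cost "is standardized to be equal to average intervention cost per patient in a study arm". A second reason for the exclusion follows: "this intervention cost will exclude the cost to purchase, store and administer vaccines, which is assumed to be identical among all practices". The control-arm figure is derived from it: "Applying the same assumption, the average cost for the control group" is zero. The result is to be set against thresholds such as two published medians for influenza vaccination programmes, $51 and $125, with one-way and probabilistic sensitivity analyses.

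**The concern.** The second reason treats vaccine costs as equal across practices and therefore as dropping out of the comparison. What a practice spends on vaccine per patient depends on the unit cost and on how many patients are vaccinated. The intervention is meant to change the number vaccinated, and the ICER divides by that change. Equal unit costs do not give equal spending per patient.

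From a health-system perspective, extra doses bought and given are an incremental cost to the extent that the system pays for them. Section 2, under Barriers to Vaccination, itself lists purchase and storage among the system barriers, and says that most women vaccinated in pregnancy are vaccinated by their OB/GYN. At stake is whether the sustainability statement rests on a figure that covers what a health system would pay. If the vaccine cost is taken to cancel, the planned one-way analyses have no reason to vary it, although it moves a health-system ICER one for one.

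**Working it through.** The documents state no ICER, programme cost or cost per dose, so there is no figure to reproduce. The check is algebra on the plan's own formula, followed by an illustration.

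**Inputs**
- I: programme cost per study-arm patient. No value is given.
- pS and pC: vaccination rates in the study and control arms; d = pS − pC. For illustration only, pC = 0.50 and d = 0.08, the planning values in the Power Analysis paragraph of Section 17, so pS = 0.58.
- Unit of effect: a vaccinated patient, not a dose ("The primary outcome (receipt of 1+ COVID vaccine) is binary").
- c: net variable vaccine cost per dose borne by the health system. Not given; assumed below.
- q: doses per additional vaccinated patient, taken as the same for vaccinated women in both arms. Not given; assumed 1 or 2.

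**Step 1. Planned ratio.** (I − 0)/d = I/d.

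**Step 2. Put uptake-dependent vaccine cost into both arms.**
[(I + c·q·pS) − (0 + c·q·pC)]/d = I/d + c·q.
The added term does not depend on I, d or pC.

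**Step 3. A worked case.** Take I = $4.08, so the planned ratio is 4.08/0.08 = $51. This start is chosen only because it equals one of the benchmarks; it is not a forecast. Assume c = $50 and q = 1. Vaccine cost per patient is 50 × 0.58 = $29.00 in the study arm and 50 × 0.50 = $25.00 in the control arm. The unit cost is identical, yet the arms differ by $4.00 per patient. The full ratio is (4.08 + 4.00)/0.08 = $101, which is 51 + 50.

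**Step 4. Range over assumed values, starting from $51.**

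| Assumed gross variable cost per dose | System bears all, q = 1 | System bears all, q = 2 | System bears half, q = 1 |
|---|---|---|---|
| $20 | $71 | $91 | $61 |
| $50 | $101 | $151 | $76 |
| $100 | $151 | $251 | $101 |
| $150 | $201 | $351 | $126 |

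If reimbursement or free supply covers the cost exactly, c = 0 and the ratio stays at $51. If reimbursement exceeds the cost, c is negative and the ratio falls.

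**Step 5. When the stated reason would hold.** Vaccine spending per patient is equal in the two arms if d = 0, in which case the ICER is undefined, or if the cost does not vary with uptake (fixed storage, for example), or if the net cost to the system is zero. Identical unit cost across practices is none of these.

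**The case against.** The best defence is that the plan declares the exclusion openly and gives a separate reason for it, comparability with earlier reminder and educational programmes. On that reading the numerator is programme cost, and control practices have none because they receive no programme during the study. Deleting the clause about identical costs would change no planned number. This stands: the ratio is a valid narrower measure and is not miscalculated. It does not rescue the cancellation argument, and it does not make a programme-only ratio a full health-system ICER.

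A reader might infer that the ICER is understated by the full cost of a dose. The documents do not support that. The outcome counts women with at least one dose, so the omitted term may be more than one dose. It may also be less, zero or negative, because the documents say nothing on reimbursement, free supply or who pays for doses given outside the practice, and some storage cost may be fixed.

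A reader might also infer that the corrected figure would cross $51 or $125. That would need a programme cost, which the documents do not give. It would also need benchmarks costed with vaccine included, and the documents do not say how the two medians were costed. If they exclude vaccine costs, comparing a vaccine-inclusive ratio with them mixes definitions.

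Finally, it may be said that programme cost alone is a fair input to a judgement on sustainability. It is, which is why both figures should be reported and neither dropped.

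**Conclusion.** Wrong as written, in the cancellation rationale only, and confined to the secondary economic analysis. Equal unit vaccine cost does not cancel from a ratio whose denominator is a difference in uptake. The planned ratio falls short of the declared health-system ICER by exactly c × q, whatever the programme cost, effect size or control rate. That identity assumes the same c and q in both arms; more generally, q is the arm difference in doses per patient divided by the difference in vaccination rate.

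The size and sign in dollars cannot be determined from the documents. The figures in the table rest on assumed costs per dose and an assumed starting ratio, and they show sensitivity rather than a likely error. Neither an understatement by a whole dose cost nor a crossing of either benchmark is established. The primary outcome, its model and the total programme cost are untouched.

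**What to change.** In the Cost-Effectiveness paragraph of Section 17:

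1. Delete the rationale that vaccine costs are identical across practices. State instead that control cost is zero because controls receive no programme.
2. Label the current ratio a programme-only ICER, meaning programme cost per additional vaccinated patient. Compare it with $51 and $125 only after confirming that those medians also exclude vaccine costs.
3. Add c × q as a parameter in the one-way and probabilistic analyses already planned, and report health-system ICER = programme-only ICER + c × q. Define c as net of reimbursement and free supply, limited to variable costs and to doses that the system provides. The vaccination dates listed in Table 5 could inform q; c needs an outside source and a stated range.
4. State the sustainability implication with both figures.

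The cost is one added model parameter, a source for it, and a few sentences of text. The reported cost per additional vaccination may become less favourable. No trial procedure changes.
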